**Table 5: Data Presented in General Listings**

Listing	Data Presented
Discontinued Subjects	Date of discontinuation Reason for discontinuation

Listing	Data Presented
Subjects with Protocol Deviations	Date of deviation Common deviation term Classification (Major/Minor)
Subjects Excluded from Efficacy Analysis 	Reason for exclusion
Demographic Data	Subject initials Date/time of informed consent Date of birth Age Sex Race Height (cm) Weight (kg) BMI (kg/m  ) Smoking status Number of years smoked Number of cigarettes smoked per day
Baseline Disease Characteristics	Time from onset of illness to first study drug intake (hours) Virus infection(s)
Prior Medication Concomitant Medication	Reported medication term Standard medical name Level 4 ATC term Indication Start date Stop date Dose Dose Unit Frequency Route
Medical History Concomitant Diseases	Reported disease, condition or surgery term Standard medical name System organ class Year of diagnosis Active at screening (Y/N) Medication therapy (Y/N)
Treatment Exposure Data	Total number of days on therapy Number of tablets taken Number of tablets dispensed Number of tablets returned Number of tablets missed

 Subjects who are not included in the ITT population due to negative RT-PCR assay will not be considered excluded from efficacy analysis

## 11. EFFICACY

### 11.1. General

Unless otherwise specified, all statistical tests will use two-sided tests at the  $\alpha=0.05$  level.

The following definitions will apply to multiple efficacy analyses:

Daily Diary Period	Each daily diary period will begin 24 hours prior to the time of diary assessment and end at the time of diary assessment.
Symptom Relief Medication	Any medication taken for a symptom of colds as indicated by the subject during the study period.

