5.10. Electronic Subject Diary

Electronic subject diaries will be completed twice daily through Day 21. The electronic diaries will capture the following information:

1. Medication intake (twice daily at time of medication intake).
2. Oral temperature (twice daily at time of medication intake). Use standard electronic oral thermometer provided by Sponsor.
3. Use of other medications taken by the subject not previously captured in the subject's medication history. Document in detail including dose in milligrams or other applicable units, time of ingestion, and the reason for use of the medication (at time of medication intake).
4. FLU-PRO Questionnaire (once daily between 7 pm and 11 pm) to characterize symptoms.
5. Activity assessment using an 11-point visual analog scale (0= unable to perform normal activity, 10= fully able to perform normal activity) (once daily between 7 pm and 11 pm).
6. Adverse experiences (once daily between 7 pm and 11 pm).

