#### Definitions:

Symptom Response	The set of criteria to be defined based upon a blinded review of symptom scores (pooled for all ITTI subjects without regard to treatment group assignment) that correlate to the time at which subjects report that they return to usual health (a daily global assessment question). Methodology to be used for the derivation of the Symptom Response definition is described in Section 11.2.1 below. Symptom scores must be maintained at the defined level for at least 2 daily diary periods without any symptom relief medication during or between those 2 daily diary periods.
Time of Symptom Response	The start of the first daily diary period in which Symptom Response is achieved and is maintained for at least two daily diary periods without any symptom relief medication during or between those two daily diary periods.
Time to Symptom Response	Time (hours) from the first dose of study medication to the Time of Symptom Response.

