#### **11.2.2. Analysis of the Primary Efficacy Parameter**

The primary efficacy parameter, time to Symptom Response, will be derived as follows:

Event: Time of Symptom Response – time of the first dose

Censored: Time of last symptom assessment – time of the first dose

If Symptom Response is achieved at the time of the first symptom assessment diary record, the subject will be excluded from the analysis.

If Symptom Response is not achieved prior to a subject’s last available diary assessment, but the criteria are met at the last available diary assessment with no evidence of symptom relief medication intake during that diary period, time of Symptom Response will be considered to have occurred at the start of the last daily diary period.

Time to Symptom Response for the NTZ treatment group will be compared to that of the placebo treatment group using a Gehan-Wilcoxon test stratified by (1) time from onset of illness to time of first dose of study medication (0-24, >24-≤36, or >36 hours from onset), (2) pre-enrollment use of symptom relief medication, and (3) presence of underlying lung condition including asthma, COPD, or past or present history of smoking. The comparison will be graphically depicted using Kaplan-Meier curves.

Analysis Population(s): ITTI

Derived Variables: Event: Time of Symptom Response – time of first dose

Censored: Time of last symptom assessment – time of first dose

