#### 11.5. Exploratory Efficacy Analyses

##### 11.5.1. Time to Individual Symptom Response

###### Definitions:

Individual Symptom Response For each individual symptom (n=32), a score of ≤ the maximum response value specified by the Symptom Response definition maintained for at least two consecutive daily diary periods without symptom relief medication during or between those daily diary periods.

Time of Individual Symptom Response

The start of the first daily diary period in which Individual Symptom Response is achieved and is maintained for at least two daily diary periods without any symptom relief medication during or between those two daily diary periods.

Time to Individual Symptom Response	Time (hours) from the first dose of study medication to the Time of Individual Symptom Response.
-------------------------------------	--

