## Time of FLU-PRO Domain Response

The start of the first daily diary period in which FLU-PRO Domain Response is achieved and is maintained for at least two daily diary periods without any symptom relief medication during or between those two daily diary periods.

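### If a FLU-PRO is completed on the evening of Day 1 after dosing, the SAP dates a response first met there before the first dose, and no rule handles the negative time

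*SAP*

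**What the plan says.** SAP 11.1 gives the definition used across the diary endpoints: "Each daily diary period will begin 24 hours prior to the time of diary assessment and end at the time of diary assessment".

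Three families of endpoints take the beginning of that period as the moment of response:

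- Primary (SAP 11.2): "The start of the first daily diary period in which Symptom Response is achieved and is maintained for at least two daily diary periods"
- The 32 items (SAP 11.5.1): "The start of the first daily diary period in which Individual Symptom Response is achieved"
- The 6 domains (SAP 11.5.2): "The start of the first daily diary period in which FLU-PRO Domain Response is achieved"

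The event time is then a simple difference, for the primary "Event: Time of Symptom Response – time of the first dose", with the same form for items and domains. The only guard near time zero is in SAP 11.2.2, with parallel text in 11.5.1 and 11.5.2: "If Symptom Response is achieved at the time of the first symptom assessment diary record, the subject will be excluded from the analysis".

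On timing, protocol 5.2 has the subject complete a FLU-PRO in the clinic on Day 1. It lists this ahead of randomization and of the observed first dose. Protocol 5.10 then schedules the "FLU-PRO Questionnaire (once daily between 7 pm and 11 pm) to characterize symptoms", and says "Electronic subject diaries will be completed twice daily through Day 21". It names the last diary day but not the first evening.

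The SAP dates ability to perform normal activities (11.4.1) and return to usual health (11.5.3) differently, at the diary entry itself.

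**The concern.** Time from first dose cannot be negative, yet a 24-hour look-back from an entry made less than 24 hours after dosing must begin before the dose. A subject who is above the limit in the clinic and meets it that evening is not a responder at the clinic entry. If the clinic entry is the first record, the exclusion rule passes over this subject, and the event time comes out below zero.

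The SAP neither floors such times nor says what to do with them. Survival routines commonly treat a negative time as invalid and leave the record out. The subjects lost would be the fastest responders, so Kaplan-Meier curves and medians would move later. Single items that can clear within hours are the most exposed. For the primary, all 32 items must be within their limits at once, in subjects who enter with moderate or severe rhinorrhea, so a same-evening response should be rare. The documents give no data to put a number on that.

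**Working it through.** The plan states no figure on this point, so there is nothing to reproduce. The check is clock arithmetic on the plan's definitions.

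**Inputs**

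- Look-back: 24 h (SAP 11.1).
- Evening entry time E on Day 1: 19 to 23 h on the clock (protocol 5.10).
- Time of first dose D on Day 1: the documents give no clock time. Assumed 8 to 17 h, then varied.

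**Formula.** Time to response = (E − 24) − D = (E − D) − 24. For an entry after the dose on the same day, E − D lies between 0 and 24, so the result is negative whatever the clinic hours. Only its size depends on D.

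**Day 1 evening entry**

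| First dose | Entry at 7 pm | Entry at 11 pm |
|---|---|---|
| 8 am | 19 − 24 − 8 = −13 h | 23 − 24 − 8 = −9 h |
| 12 noon | 19 − 24 − 12 = −17 h | 23 − 24 − 12 = −13 h |
| 5 pm | 19 − 24 − 17 = −22 h | 23 − 24 − 17 = −18 h |

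The range is −22 to −9 h for doses between 8 am and 5 pm. For any dose from midnight to 7 pm it is −24 h (19 − 24 − 19) to −1 h (23 − 24 − 0).

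**First evening entry on Day 2 instead.** Adding 24 h gives +2 to +15 h for doses between 8 am and 5 pm, and 0 to +23 h for any dose up to 7 pm. No negative time arises.

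**Dating at the entry, as in SAP 11.4.1 and 11.5.3.** A Day 1 evening response would fall at E − D = +2 to +15 h for doses between 8 am and 5 pm, so those two endpoints are not affected.

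**What happens to the subject depends on two things the documents leave open**

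| Day 1 evening FLU-PRO | First record is | Result for a Day 1 evening responder |
|---|---|---|
| Yes | Pre-dose clinic entry | Negative time, no rule |
| Yes | Day 1 evening entry | Excluded, on an outcome seen after dosing |
| No | Pre-dose clinic entry | Case does not arise |

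**Illustration of losing these subjects.** All inputs here are assumptions: an item median of 96 h, a share p who first meet the limit on the Day 1 evening, and exponential times with rate L for the rest. L solves (1 − p)·exp(−96L) = 0.5, and the median after dropping the share is ln 2 / L = 96·ln 2 / ln(2(1 − p)).

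- p = 0.05: 96 × 0.6931 / 0.6419 = 103.7 h
- p = 0.10: 96 × 0.6931 / 0.5878 = 113.2 h
- p = 0.20: 96 × 0.6931 / 0.4700 = 141.6 h

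This shows how one pooled median could move. It says nothing about the difference between arms.

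**The case against.** The strongest objection is that the premise is not established. Protocol 5.10 asks for one FLU-PRO a day, and one has already been done in the clinic on Day 1, so a second that evening may never be due. If the first evening entry is on Day 2, nothing goes wrong. This stands, and the point has to be conditional. On the other side, 5.10 makes no exception for Day 1, and site review of entries begins on Day 2 (protocol 5.3), which fits entries made the evening before. Neither text decides it.

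Second, the first symptom record could mean the first evening entry, in which case the exclusion already removes these subjects. The SAP does not define the term. The clinic entry is the more natural reading, because it comes first and because SAP 11.6.2 uses baseline FLU-PRO scores as analysis data. The other reading would exclude subjects on a post-treatment outcome, so the term needs a definition either way.

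Third, the rule is the same in both blinded arms, and the item and domain analyses are exploratory and outside the testing hierarchy of SAP 11.4. This stands and limits the severity.

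A reader might also infer that the look-back lets cold medication taken before enrollment block a Day 1 response. The documents do not support that firmly. SAP 11.1 can be read as limiting symptom relief medication to the study period, and pre-enrollment use is handled separately as a stratification factor.

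**Conclusion.** The point holds conditionally and is of low severity. If a FLU-PRO is completed on the evening of Day 1 after dosing, a response first met there is always given a time before the first dose. The first-record exclusion misses it when that record is the pre-dose clinic entry, and nothing says how a negative time is treated. The sign follows from the SAP's definitions. The size of 9 to 22 h rests on assumed dosing hours of 8 am to 5 pm, and widens to 1 to 24 h for any dose up to 7 pm.

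A reader might infer that the plan is certain to produce negative times, or that the primary result is at risk. The documents support neither. They do not settle whether the Day 1 evening entry exists, and the primary needs all 32 items within limits that same evening. Nor is there a demonstrated effect on the treatment contrast, type I error or power. The 96 h median and the shares of 5, 10 and 20% are illustrative and come from outside the documents.

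**What to change.** Leave the diary-period definition in SAP 11.1 as it is. It also sets the medication-free windows in 11.2.1, 11.4.1 and 11.5.3, so editing it there would reach the derivation of the primary response definition and two endpoints that do not have this problem.

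In SAP 11.2, 11.5.1 and 11.5.2, define the time of response as the later of (a) the start of the qualifying diary period and (b) the time of first dose. Apply the same floor where a response is credited on the last available diary, since that rule also dates to the start of the period. A Day 1 evening responder then stays in as an event at 0 h. Responses whose period starts after the first dose are unchanged.

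State that the first symptom assessment diary record is the pre-dose baseline entry, and state whether the first evening FLU-PRO falls on Day 1 or Day 2. If it is Day 2, the floor changes nothing for doses up to 7 pm.

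The cost is a few sentences in the SAP and a one-line change to the derivation program, made before unblinding. No data collection changes.

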### 11.2. Primary Efficacy Analysis: Time to Symptom Response

The primary efficacy analysis will be the comparison of the time from first dose of study medication to Symptom Response between treatment groups using Kaplan-Meier survival curves and a Gehan-Wilcoxon test stratified by (1) time from onset of illness to time of first dose of study medication (0-24, >24-≤36, or >36 hours from onset), (2) pre-enrollment use of symptom relief medication, and (3) presence of underlying lung condition including asthma, COPD, or past or present history of smoking. Separate Symptom Response definitions will be determined for ITTI subjects with no underlying lung condition and for ITTI subjects with underlying lung conditions. Time to Symptom Response will be calculated in the same way for the two groups and all ITTI subjects will be analyzed together.

#### Definitions:

Symptom Response	The set of criteria to be defined based upon a blinded review of symptom scores (pooled for all ITTI subjects without regard to treatment group assignment) that correlate to the time at which subjects report that they return to usual health (a daily global assessment question). Methodology to be used for the derivation of the Symptom Response definition is described in Section 11.2.1 below. Symptom scores must be maintained at the defined level for at least 2 daily diary periods without any symptom relief medication during or between those 2 daily diary periods.
Time of Symptom Response	The start of the first daily diary period in which Symptom Response is achieved and is maintained for at least two daily diary periods without any symptom relief medication during or between those two daily diary periods.
Time to Symptom Response	Time (hours) from the first dose of study medication to the Time of Symptom Response.

#### Variables Used for the Analysis

The primary efficacy analysis will require the following variables:

**Table 6: Variables Used for the Primary Efficacy Analysis**

Variable	Source	Format/Notes
Date and time of first medication intake	CRF	

Variable	Source	Format/Notes
Date and time of completion for each symptom assessment record	Subject diary	
Symptom score assessment for each symptom for each diary record	Subject diary	
The ordinal symptom severity, intensity or frequency score assessment for each of the 32 symptoms will be coded to numerical values 0-4.
 
It will not be possible for any individual symptom assessment to be missing within a diary record, therefore no individual item imputation will be required.
 
In the event that the diary was not completed at a specified time point (e.g., Day 2), the missing data will not be imputed.

Date and time of symptom relief medication intake	Sponsor-provided listing	The list of symptom relief medications will be selected from the listing of all concomitant medications prior to unblinding.

#### 11.2.1. Derivation of the Symptom Response Definition

Two Symptom Response definitions will be derived based upon analysis of blinded daily FLU-PRO symptom scores and responses to the daily FLU-PRO question, “Have you returned to your usual health today?” for (1) the ITTI population with underlying lung conditions and (2) for the ITTI population without underlying lung conditions.

The Symptom Response definition will consist of a maximum response criterion (0,  $\leq 1$ ,  $\leq 2$ ,  $\leq 3$  or  $\leq 4$ ) for each of the 32 FLU-PRO items.

The objective of this procedure is to identify the Symptom Response definition that minimizes the diary-level misclassification rate between Symptom Response and Usual Health status as reported by the EV/RV-positive subjects enrolled in this study.

Procedure:

1. Evaluate whether each daily diary record has achieved return to usual health (requiring 2 consecutive daily diary assessments with “yes” response to the “usual health” question in FLU-PRO without use of symptom relief medication during or between those daily diary periods). This step will create a “Returned” variable with possible values of “Y” for each daily diary record that constitutes return to usual health and “N” for each daily diary record that does not.
2. Determine the set of Symptom Response definitions to be evaluated by selecting potential maximum response criteria that are likely to correlate well with return to usual health.
  - a. Examine the cumulative distribution of ordinal symptom assessment responses for the first two consecutive diary records at which subjects return to Usual Health.

b. Maximum response criteria will be selected for consideration as part of the Symptom Response definition if they are included in the  $\geq 90\% - \leq 95\%$  cumulative distribution of symptom assessments at the time of return to usual health. If a maximum response criterion includes the 95th percentile and exceeds the 95% cumulative distribution, the criterion will still be selected for consideration.

For example, consider the following cumulative distribution of symptom ratings for the two consecutive diary records at which a fictional population of subjects return to usual health:

		Records Reporting 0	Records Reporting $\leq 1$	Records Reporting $\leq 2$	Records Reporting $\leq 3$	Records Reporting $\leq 4$
Coughing	N	300	455	478	485	500
	%	60.0%	91.0%	95.6%	97%	100%
Felt cold	N	480	499	500	500	500
	%	96.0%	99.8%	100%	100%	100%
(table would include all 32 FLU-PRO symptoms for maximum response criteria selection purposes)						

For “coughing”, the maximum symptom response criteria of  $\leq 1$  and  $\leq 2$  would be selected because the 90th percentile of responses is included in  $\leq 1$  and the 95th percentile is included in  $\leq 2$ . For “felt cold”, the maximum symptom response criterion of 0 would be selected because both the 90th and 95th percentiles are included in 0.

Possible Symptom Response definitions will be determined from the set of maximum response criteria selected.

3. For each possible Symptom Response definition, evaluate whether each daily diary record has achieved Symptom Response (two consecutive diary entries with all symptoms assessed  $\leq$  the maximum response values with no symptom relief medication intake during or between those two daily diary periods). This step will create a “Responded” variable with possible values of “Y” for each daily diary record that has achieved Symptom Response and “N” for each daily diary record that has not achieved Symptom Response. This step will be performed on a data storage/VM infrastructure that can support evaluation of 4.2 billion daily diary records with different possible Symptom Response definitions. If the number of diary record evaluations required (number of possible Symptom Response definitions multiplied by number of daily diary records to be evaluated) exceeds 4.2 billion, go back to step 2b above, and increase the  $\geq 90\%$  cumulative distribution threshold by 0.1% increments until the number of possible maximum response criteria is reduced to a number that will result in evaluation of  $\leq 4.2$  billion daily diary records.
4. For each possible Symptom Response definition, determine the definition’s misclassification rate by comparing the “Responded” and “Returned” variables for each daily diary record. The percentage of daily diary records with mismatched “Responded” and “Returned” values (e.g., “Y” and “N”) will constitute that Symptom Response definition’s misclassification rate.

5. The Symptom Response definition returning the lowest misclassification rate will be selected as the Symptom Response definition for the study and will be used to calculate the primary efficacy parameter (time to Symptom Response) for each subject.
6. If two or more Symptom Response definitions produce the lowest misclassification rate (a “tie”), the Symptom Response definition with the lower sum of scores will be selected. In the event that the sum of scores are also equal, the Symptom Response definition with the smallest absolute difference between the proportion of false positives (“Responded” but not “Returned”) and false negatives (“Returned” but not “Responded”) will be selected. If there is still a tie, the definition with the lowest sum of maximum response values for the Body/Systemic domain will be selected, and if that is still a tie, the definition with the lowest sum of maximum response values for the Eye domain will be selected, and so on for the Gastrointestinal, Throat, Nose and Chest/Respiratory domains. If there is still a tie, list the items under the Body/Systemic, Eye, Gastrointestinal, Throat, Nose and Chest/Respiratory domains in alphabetical order and compare the maximum response values until a definition with the lowest item score can be selected.

The Symptom Response Definition selected in this step will be applied for any subsequent analysis that calls for the primary efficacy analysis to be repeated unless otherwise specified.

#### **11.2.2. Analysis of the Primary Efficacy Parameter**

The primary efficacy parameter, time to Symptom Response, will be derived as follows:

Event: Time of Symptom Response – time of the first dose

Censored: Time of last symptom assessment – time of the first dose

If Symptom Response is achieved at the time of the first symptom assessment diary record, the subject will be excluded from the analysis.

If Symptom Response is not achieved prior to a subject’s last available diary assessment, but the criteria are met at the last available diary assessment with no evidence of symptom relief medication intake during that diary period, time of Symptom Response will be considered to have occurred at the start of the last daily diary period.

Time to Symptom Response for the NTZ treatment group will be compared to that of the placebo treatment group using a Gehan-Wilcoxon test stratified by (1) time from onset of illness to time of first dose of study medication (0-24, >24-≤36, or >36 hours from onset), (2) pre-enrollment use of symptom relief medication, and (3) presence of underlying lung condition including asthma, COPD, or past or present history of smoking. The comparison will be graphically depicted using Kaplan-Meier curves.

Analysis Population(s): ITTI

Derived Variables: Event: Time of Symptom Response – time of first dose

Censored: Time of last symptom assessment – time of first dose

